3.4.1 Inclusion Criteria

Veteran Inclusion Criteria:

- 1) Confirmed PD diagnosis in the VA medical record;
- 2) Primary Major Depression, Dysthymia, or Depression NOS of at least moderate severity per the SCID;⁸⁷
- 3) Access to a computer/tablet with high-speed internet access. Comorbid anxiety disorders are not exclusionary if the depressive disorder is primary.
- 4) Ages 35-85;
- 5) Stable medication and mental health regimen (including applicable antidepressants, other psychotropic agents, movement disorder drugs, clinic-based psychotherapies) \geq 6 weeks). This means that the medication regimen and treatment plan have been consistent for at least 6 weeks.
- 6) Family member or friend willing to participate;

Veteran Exclusion Criteria:

- 1) Possible dementia or marked cognitive impairment [Montreal Cognitive Assessment Score (MoCA) $<$ 21].¹⁷
- 2) Motor fluctuations \geq 50% of the day;
- 3) Acute suicidal plans or intent (determined by clinical interview);
- 4) Unstable medical conditions;
- 5) Bipolar, Psychotic Spectrum, or Substance Use Disorders.

Exclusion Criterion 1 above is due to dementia being associated with numerous clinical variables (e.g., motor fluctuations, delusions) that make the rating of depression difficult. Dementia may also compromise the clinical effectiveness of a non-pharmacological treatment due to its impact on cognitive processes. As dementia is not typically seen in the early stages of PD, results from the current study should generalize to the larger PD population without dementia.

Care-partner Inclusion Criteria:

- 1) Ages 25-85;
- 2) Daily contact with Veteran

Care-partner Exclusion Criteria:

- 1) Unstable medical/psychiatric conditions (clinical interview).

3.4.3 Subject Recruitment and Consent

180 participants (90 Veterans with PD and 90 Care-partners) will be recruited from the New Jersey area (2 VAMCs and 9 CBOCs), using several recruitment strategies. A DSS report will be generated with contact information of Veterans in VANJ who had a visit with a diagnosis of PD, during the previous 4 fiscal years (a HIPAA waiver has been submitted). Letters will be mailed informing them of the study, and study staff will contact them by telephone to determine if they would be interested in and eligible to participate. If there is no contact by the Veteran, the research team will call the Veteran after waiting a period of 2 weeks, unless the veteran notifies the study team that he/she does not wish to receive a phone call.

Recruitment will also take place through Neurology and Primary Care Clinics at VA New Jersey. Veterans will be recruited from these sites via recruitment flyers (attached). Also, providers may refer potential candidates to the research team. This will be done by either instructing the Veteran to contact the research team or alerting the research team via CPRS that the Veteran is interested. In case of the latter, the research team will send a letter (see attached) to the potential candidate that includes the name of the referring provider. As above, phone contact will not be initiated earlier than two weeks and in cases where the Veteran notifies the study team that he/she does not wish to be contacted.

Candidates identified with the methods described above will be informed of the study. If they are interested, a phone script will guide the candidate through informed consent for the phone screen (see attached Waiver of documentation of consent). If verbal consent is provided, they will be screened by telephone (see attached phone screen) for basic eligibility criteria. For those who meet basic eligibility and remain interested, consent forms will be mailed to potential participants. At a later time (allowing for consent forms to arrive at candidate's homes), study staff will then review the consent form with the potential participant over the phone. After all questions are answered, the participant will sign the consent form and mail it back to the study team, so that they can later be formally evaluated for study eligibility (i.e., baseline evaluation). This same consent process will also be conducted for the Care-partner.

Other Procedures:

Baseline Assessment: After the screening and consent, appropriate individuals will be scheduled for a telephone appointment. Demographic information will be obtained, and inclusion/exclusion criteria will

be assessed. A detailed medical (i.e., number of medical conditions, duration and stage of PD) and psychiatric history (i.e., number past depressive episodes, past treatments), and a current list of all prescription and over-the-counter medications will be gathered. Clinician-administered rating scales and self-report measures will be completed. The screening appointment typically lasts between 2 and 3 hours. If participants are unable to complete the entire screening evaluation in one day, a second telephone appointment will be scheduled within the next 7 days to complete the remainder of the screening procedures.

Randomization: All appropriate candidates will be randomly assigned to receive either: 1) telehealth-based cognitive-behavioral therapy plus standard care (the “intervention”) or 2) standard care, based on computer generated random assignment, after the screening appointment (the “control group” treatment). Randomization will be stratified by antidepressant medication (ADM) use at baseline (yes or no) such that patients taking ADMs are equally represented in both treatment conditions. Patients will be notified of their assignment to group via telephone in the week following their baseline assessment.

Assessments: Participants will be assessed at baseline (week 0), midpoint (week 5), endpoint (week 10), and follow-up (1 and 6 months post-treatment). Follow-up assessments will be conducted via telephone for the clinician-rated instruments (i.e., HAM-D, HAM-A). Self-report questionnaires will be mailed to participants with a self-addressed envelope that can be returned to the research team upon completion. If participants request assistance with the self-report questionnaires, they will be mailed to them and also read aloud to them by telephone. These assessments will last 1-2 hours.

Qualitative Data: Semi-structured interviews will be used to study participants’ perspectives in terms of treatment effectiveness. Specifically, selecting from the study’s treatment arm, quantitative data will be used to identify a purposive subsample of participants for qualitative interviews, where 10 Veterans who respond at endpoint (i.e., CGI-I of 1 or 2) and 10 who do not respond (i.e. CGI-I of 4 or 5) to TH-CBT will be identified. Once identified, qualitative data will consist of semi-structured interviews conducted separately with these Veterans and their Care-partners. A total of 40 interviews will be conducted (10 responder Veterans + their 10 Care-partners; 10 non-responder Veterans + their 10 Care-partners).

Blinding: All follow-up (i.e., post-baseline) assessments will be conducted by independent evaluators without knowledge of treatment condition. Veterans will be instructed not to reveal group assignment to raters. Veterans and therapists will not be blind given the nature of the treatment. Information regarding the integrity of the blind (patient revealing group assignment to rater) and the blind raters’ guess regarding group assignment will be collected after each study evaluation. In rare cases in which the blind may be broken, the interview recording (with unblinding information removed) will be presented to a second rater for coding. Therefore, all final score determinations will be made by an independent evaluator with no knowledge of group assignment.

Video-to-home telehealth V2H: Inclusion criteria require that all participants will need a home computer or tablet with a webcam to participate in the study. If they do not have a webcam, one will be provided to them. V2H set up for Veterans will follow established procedures in place at VANJ, which is supported by the facility’s telehealth lead (██████████). This includes signing the facility’s video-to-home consent form and application, documenting which records are needed, including emergency contacts for the participant (included as an attachment). Veterans will need to download the software (i.e., Jabber) for connecting with the study team. They will be assisted with self-help instructions, study team telephone guidance, and/or a home visit, depending on the level of assistance needed with V2H installation procedures.

As documented in the VHA's Clinical Video Telehealth in the Home Manual, prior to the initiation of telehealth sessions, information will be obtained pertaining to emergency contacts that can be called in case of emergency.

Contact for appointments related to treatment and assessments:

This research is being carried out with a population that requires active engagement to mental health services. In standard VA NJ mental health care, this is reflected in policies requiring at least three follow-up phone calls and/or a letter after a no-show to standard mental health appointment. Our research team will adopt a similar approach to maintaining engagement, utilizing telephone calls and letters to arrange for appointments. Our philosophy will be guided by a person-centered, relationship-building approach. For example, we anticipate that there will be several missed appointments and our interactions with study participants will convey empathy and understanding for missed appointments, as well as flexibility and accommodation for rescheduling. On the other hand, our research staff will also be sensitive to indications that participants no longer wish to participate and will cease contact efforts once that appears to be the case.

3.4.5 Subject Costs and Compensation

There will be no cost to subjects for the study treatment sessions. Veterans and Care-partners will each receive \$45 per outcome assessment completed. Subjects selected for the semi-structured interviews will receive an additional \$20.

3.5 Chart Review Selection

Research staff will also perform retrospective chart reviews on all enrolled study subjects for the purpose of documenting the standard care that participants received during the study. Standard care will focus on mental health standard care. Because our study occurs within the context of standard care, data will be collected to describe the standard care received and/or control for potential standard care covariates. Specifically, we will gather detailed standard VA medical care information pertaining to: a) psychotropic medication use (dose, type, frequency); b) number of medication management visits; c) number of standard care psychotherapy visits (i.e., non-TH-CBT). Non-VA standard mental health care will be assessed via interview.

As with our primary data, all medical records data will have identifiers removed and data storage will occur by ID number, rather than name. Also, the data will be stored on a secure server that is maintained by the VA's IRM (Information Resource Management) and has up to date security protections. Within this server, the data will be placed on a secured folder [REDACTED] that is restricted for only users that are part of the VANJHCS Dual Diagnosis Unit, which is our local research unit. Data will also be stored in VINCI, which is the VA's computer infrastructure that allows data storage, analysis, and sharing, while maintaining privacy and security.

4. Study Variables

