3.3 Sample Size Justification & Subject Selection

The study will enroll a total of 180 subjects (90 Veterans + 90 of their Care-partners), from VA New Jersey, who have Parkinson's Disease and depression. 1,199 Veterans with dPD were served in VA New Jersey during the last four fiscal years. Several methods of recruitment (see Recruitment and Consent below) will be used to enroll this pool of Veterans.

Our Power Analyses assume 180 participants (90 enrolled dyads) with 144 participants (72 dyads, 36 dyads each arm), completing the study. Observed standard deviations in the power calculations that follow are taken from control group baseline data in [name] et al.¹⁶ For the primary test of treatment differences in HAM-D scores, controlling for baseline HAM-D scores and demographic covariates, the current study is powered to detect a 2.5 point HAM-D treatment difference between groups. For comparison, we observed a group difference of 7.30 in [name] et al.¹⁶ For the secondary test of responder/nonresponder, we considered clinical response rates of 0.05 and 0.10 for the control group and .35, .40, and .45 for the treatment group. Power was greater than .95 in all cases. For comparison, we observed rates of 0.08 and 0.56 in the control and treatment groups, respectively, in [name] et al. (2011).

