4.1 Interventions

Study Conditions

Control Group: Standard Care. Standard Care is defined as medical and psychiatric treatment provided by patients' personal doctors (e.g., neurologists, psychiatrists, therapists). Veterans will continue to receive routine clinical care and will remain on all depression treatments that they were receiving prior to their study (e.g., stable ADMs, established psychotherapy, clinical monitoring). Care-partners will continue to receive all non-clinical services for which they qualify through the VA, including services offered through the Office of Caregiver Support, as well as PD caregiving resources, support groups, and referral information provided by the American Parkinson's Disease Association.

Intervention Group: TH-CBT + Standard Care: The TH-CBT group will receive the study intervention and standard care. The study treatment has been previously manualized and modified for remote administration. dPD Veterans will receive 10 weekly individual sessions (60 minutes each) of CBT, delivered via V2H. Treatment will incorporate behavioral activation, exercise, thought monitoring and restructuring, relaxation training, worry control, and sleep hygiene (emphasis dictated by patient preference), and will be augmented with 3 separate Care-partner educational sessions (30-60 minutes each), that are evenly dispersed throughout the Veterans' treatment. The Care-partner sessions are intended to provide Care-partners with the skills needed to facilitate the Veterans' practice of self-management techniques (i.e., exercise, socializing, reframing thoughts) both between sessions and after treatment had ended, in order to empower the Care-partner in the helping role. The intervention will be provided by IRB-approved licensed clinical social workers and doctoral level clinicians under the supervision of Drs. [name] and [name].

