Unless otherwise indicated, all of the analyses below will use mixed models analysis to examine treatment effects on the specified dependent variable. There will be one between-group variable (TH-CBT versus control), one repeated measure variable (time), and group-by-time interactions (effect of interest). We will consider several correlational structures between repeated measures (e.g., compound symmetry) and determine the best structure using the Akaike's Information Criterion (AIC). Random effects will be specified for each subject. For each dependent variable, we will analyze the effect of interest (i.e., group X time) separately at each post-randomization assessment point. The models will include demographic covariates (age, sex) as indicated. Standard residual diagnostics will be applied. In the event of unaccounted-for outliers, analyses will be run with and without the outliers. Should the residuals deviate unacceptably from normality assumptions, we will use robust estimation as described and cataloged by Wilcox.³⁵

AIM 1: To evaluate the effectiveness of TH-CBT for improving Veteran outcomes in dPD. Primary Hypothesis: Depressive symptoms will decrease more for Veterans receiving TH-CBT, than for Veterans in the control group. The HAM-D is the primary depression outcome measure. Secondary Hypotheses. There will be more treatment responders in the TH-CBT group. Analyses examining depression treatment response will utilize the CGI-I (response equals CGI-I score of 1- 2).³⁶ Fisher's exact test will be used to test the hypothesis related to treatment response. A sensitivity analysis will be performed using logistic regression to examine the possible importance of covariates. Secondary Hypotheses: Secondary

outcome measures for Veterans receiving TH-CBT will show greater improvement (BDI, HAM-A, SF-36) over time than for those of Veterans in the control group. As these measures can be expected to be correlated, the significance threshold adjusting for multiple-testing will be determined by permutation-based analysis.

AIM 2: To examine the impact of TH-CBT for dPD on a variety of Care-partner outcomes. Hypotheses: TH-CBT Care-partners will feel more empowered (FES), report less distress (CDS) and be less critical (to the Veteran; PCS) relative to controls. The analysis approach will be the same as in Specific Aim 1

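### Section 3.5 permits adjustment for standard care received after randomization, which can bias the total effect of TH-CBT in either direction; confirmatory models should be limited to pre-randomization covariates

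*Combined protocol and SAP*

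**What the plan says.** Section 3.5 sets up a retrospective chart review of all enrolled subjects "for the purpose of documenting the standard care that participants received during the study". The items are the dose, type and frequency of psychotropic drugs, then "b) number of medication management visits; c) number of standard care psychotherapy visits (i.e., non-TH-CBT"). Mental health care outside the VA is asked about at interview. The stated use is that "data will be collected to describe the standard care received and/or control for potential standard care covariates". The section does not limit control to baseline values, to a particular outcome, or to a time window.

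The places that specify models say something narrower:

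- Section 3.3, on power: "For the primary test of treatment differences in HAM-D scores, controlling for baseline HAM-D scores and demographic covariates".
- Section 5, on the mixed models: "The models will include demographic covariates (age, sex) as indicated".
- Section 5, on treatment response, after Fisher's exact test: "A sensitivity analysis will be performed using logistic regression to examine the possible importance of covariates". These covariates are not named.

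Section 4.1 defines the comparison. "The TH-CBT group will receive the study intervention and standard care", and the control group receives standard care alone. Sections 3 and 3.4.3 stratify randomization by antidepressant use at baseline. Section 5 does not list that factor among its covariates.

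**The concern.** The trial asks what happens when TH-CBT is added to standard care, whatever standard care then turns out to be. That is a total effect, and randomization protects it. Care received during the study lies downstream of randomization, so conditioning on it gives up that protection.

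The protocol itself shows how care could be linked to both outcome and arm. Section 4.4 expects study monitoring to pick up worsening and lead to further care, so care can follow clinical course. Section 4.1 gives the TH-CBT arm ten weekly clinician contacts, and Section 4.3 lists linkage to treatment among the responses open to study staff, so arm could plausibly affect care. Section 4.1 has Veterans continue their existing depression treatments but does not say that new care is barred. The amendment log records an added follow-up question on psychotropic medication changes.

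Two things are at stake. An adjusted estimate may answer a different question from the one posed. And because Section 3.5 leaves the choice open, adjustment could be chosen or dropped after the results are seen. There is also a timing problem: data collection runs to the six-month follow-up, so a study-long visit count placed in a week-10 model would include care given after that outcome was measured.

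**Working it through.** The plan states no figure on this point, so there is nothing to reproduce. The check has two parts.

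**1. Do the documents permit the adjustment, and does anything close it off?** Section 3.5 names control as a purpose and fixes the timing as during the study. Sections 3.3 and 5 list baseline HAM-D, age and sex, and leave the covariates of the responder regression open. No section excludes care received or calls such adjustment exploratory. The permission is therefore open, but no specified model uses it.

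**2. What would adjustment do?** Let A be arm (1 = TH-CBT), M care use during the study, and Y the HAM-D score. For least squares,

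adjusted effect − total effect = −a × g,

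where a is the effect of A on M and g is the coefficient of M in the model containing A and M. Bias needs both a ≠ 0 and g ≠ 0.

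The illustration uses these inputs. **All are assumptions except that 2.5 points is the detectable difference in Section 3.3.**

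- Total effect −2.5 (negative is benefit).
- M = 2 + aA + uU + e, with U (unmeasured severity or help-seeking) and e each of SD 1; u = 1 if there is a shared cause, otherwise 0.
- Y = dA + bM + vU + error of SD 3, with v = 2 if there is a shared cause, otherwise 0; d = −2.5 − ab, which holds the total effect at −2.5.

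Then g = b with no shared cause. With a shared cause, g = b + uv/(u² + 1) = b + 2/2 = b + 1. The last column is a simulation of 400,000 subjects per scenario.

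| a | b | Shared cause | g | −a × g | Adjusted, formula | Adjusted, simulated |
|---|---|---|---|---|---|---|
| 0 | 0, −0.5 or −1 | no or yes | b or b + 1 | 0 | −2.50 | −2.48 to −2.51 |
| −0.5 | −0.5 | no | −0.5 | −0.25 | −2.75 | −2.76 |
| −1 | −1 | no | −1 | −1.00 | −3.50 | −3.50 |
| −0.5 | 0 | yes | 1 | +0.50 | −2.00 | −2.00 |
| −1 | 0 | yes | 1 | +1.00 | −1.50 | −1.51 |
| −1 | −1 | yes | 0 | 0 | −2.50 | −2.49 |
| +0.5 | 0 | yes | 1 | −0.50 | −3.00 | −3.00 |
| +0.5 | −1 | no | −1 | +0.50 | −2.00 | −1.99 |

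Leaving M out returned −2.48 to −2.51 in every scenario. In rows 2 and 3, care helps and TH-CBT reduces it; the adjusted figure is then the direct effect at fixed care and overstates the total benefit. In rows 4 and 5, M only marks poor course and the benefit is understated. In row 6 the two paths cancel.

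The identity is for linear models. In the responder logistic regression the same two paths operate, but adjusted and unadjusted odds ratios also differ for a separate reason, non-collapsibility, so these figures do not carry over to it.

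**The case against.** The strongest reply is that Section 3.5 is a data-collection section, not an analysis plan. It names no model, outcome or test. Where the analysis is specified, every named covariate precedes randomization, so the primary HAM-D comparison as written already disregards changes in standard care. The one open slot, the responder regression, is labelled a sensitivity analysis. Entry requires a regimen stable for at least six weeks and prior treatments continue, so a large difference in care between arms is an assumption. And asking how far co-intervention explains a result is legitimate in a trial where patients and therapists know the assignment.

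Much of this stands. A reader might infer that the primary model will adjust for care received; Sections 3.3 and 5 do not say so. A reader might also infer that adjustment necessarily removes part of the benefit; the table shows it can equally inflate it, even when TH-CBT lowers care use. Nor do the documents support a one-directional size, since they give no SD, no correlation between care and outcome, and no effect of TH-CBT on care.

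The reply does not remove the permission. Section 3.5 is the only text stating how the chart data may be used, and it names control. It cannot be read as meaning baseline care, because the review covers care during the study. Stability at entry does not fix care for the following months.

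**Conclusion.** The point holds as an open permission that should be closed, not as an error in a prespecified model. Adjusting a confirmatory comparison for care received after randomization can bias the total effect of TH-CBT plus standard care versus standard care, on two conditions: TH-CBT changes care use, and care use is related to outcome given arm. If the first fails, the bias in the linear models is zero.

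Neither direction nor size can be determined from the documents. Under the assumed paths above, the shift ran from 0 to about 1 point either way, which at its largest is 1.0/2.5 = 40% of the difference the trial is powered to detect. That shows the mechanism can matter; it is not an estimate for this trial.

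**What to change.** In Sections 3.5 and 5, state that:

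- All confirmatory treatment-effect models, and the responder logistic regression, use only pre-randomization covariates: baseline HAM-D, or the baseline value of the outcome where one exists; age; sex; and the baseline antidepressant-use stratum.
- Standard care received during the study is reported descriptively by arm.
- Any analysis adjusted for that care is labelled exploratory and is not presented as an estimate of the total effect of TH-CBT plus standard care versus standard care.

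This keeps the exploratory co-intervention question open. It also brings the stratification factor into the model, which Section 5 now omits. The cost is a few sentences. The baseline assessment and the randomization already supply these covariates, so no data collection changes and no patients are lost.
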